5.7.4 Secondary Efficacy Endpoints Evaluated with Data from the Current Study

If the co-primary endpoint tests are both significant, then the secondary endpoints are evaluated using a fixed sequence approach, with each test in the hierarchy conducted at p=0.05. See Section 5.2.5 for the testing order.

5.7.4.1 Freedom from Photophobia, Phonophobia or Nausea at 2 Hours

Freedom from photophobia, phonophobia, and nausea are assessed, by treatment group, by tabulating the number of mITT subjects who reported the presence of the symptom at migraine onset who then report the absence of the symptom at 2 hours post-dose. Subjects who report the symptom at baseline, but have missing data at 2 hours post-dose will be imputed as failures (NC=F). Also, subjects in the analysis set that take rescue medications on or before providing their 2 hours post-dose data are imputed as failures.

The principal measurement for the associated symptoms (phonophobia, photophobia, and nausea) is made on a binary scale (0 = absent; 1 = present). An exploratory measurement of these symptoms was also made on a 4 point Likert scale (0=none, 1=mild, 2=moderate, 3=severe).

For these three endpoints, the difference between treatment groups, is evaluated by computing the common risk difference, using CMH weights (sample size weights), stratified by the use of prophylactic migraine medication (yes or no). The risk difference is tested at a two-sided alpha level of 0.05. If a stratum (prophylactic medication use: yes or no) has sparse data (less than 5 subjects) then the strata are pooled.

The results presented for the analysis of each symptom include those described in items (a) through (e) for the primary analysis of pain freedom (Section 5.7.3.1). In this case, the "risk" is the probability of being free from the symptom of interest at 2 hours post-dose. In addition, the following display will be created for each of the 3 symptoms:

• A table showing descriptive statistics for the 4-point scale, which includes the number and percentage of subjects reporting each of the 4 symptom levels at 2 hours post-dose, and the percentage of subjects with missing data, for each treatment group. The table will include exact (Clopper-Pearson) 95% CIs for each percentage.

5.7.4.2 Pain Relief at 2 Hours

Pain relief at 2 hours post-dose is assessed by tabulating the number of mITT subjects that report a pain level of none or mild (responses of 0 or 1 on the 4-point Likert scale) at 2 hours post-dose, by treatment group. Subjects with missing data at 2 hours post-dose will be imputed as failures (NC=F).

The results to be presented for the analysis include those described in items (a) through (e) for the primary analysis of pain freedom (Section 5.7.3.1). In this case, the "risk" is the probability of pain relief at 2 hours post-dose.

5.7.4.3 Probability of Requiring Rescue Medication within 24 Hours

Whether or not a subject took rescue medication within 24 hours after the initial dose of study medication is tabulated, using mITT subjects, and the percentages are compared between treatment groups.

The results are presented for the analysis include those described in items (a) through (e) for the primary analysis of pain freedom (Section 5.7.3.1). In this case, the "risk" is the probability of not requiring rescue medication within 24 hours post-dose.

Rescue medications are tabulated by treatment group and overall.

Information regarding the rescue medication, including the type, date and time taken, dose, route and form of administration, and frequency, is presented in a listing by treatment group and subject.

5.7.4.4 Functional Disability Scale at 2 Hours

Impact of treatment on subject disability is assessed using a single-question, functional disability scale. Subjects rate the level of disability they perceive as a result of their migraine in performing normal actions using a 4-point scale: Normal Function, Mild Impairment, Severe Impairment, or Required Bedrest. The proportion of mITT subjects who have a response of "normal" at 2-hours post dose will be evaluated as the endpoint of interest.

The information from the 4-point scale will be directly summarized as follows:

• A table showing descriptive statistics for the 4-point scale, which includes the number and percentage of subjects reporting each of the 4 disability levels at 2 hours post-dose, and the percentage of subjects with missing data, for each treatment group, using the observed data. The table will include exact (Clopper-Pearson) 95% CIs for each percentage.

The results to be presented for the analysis include those described in items (a) through (e) for the primary analysis of pain freedom (Section 5.7.3.1). In this case, the "risk" is now the probability of a functional disability level of "normal" at 2 hours post-dose.

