1.4 Study Rationale

Migraine is a chronic and debilitating disorder characterized by recurrent attacks lasting four to 72 hours with multiple symptoms, including typically one-sided, pulsating headaches of moderate or severe pain intensity that are associated with nausea or vomiting, and/or sensitivity to sound (phonophobia) and sensitivity to light (photophobia). The World Health Organization's (WHO) Global Burden of Disease Study ranks migraine as the third most prevalent disease worldwide [9] and the Global Burden of Disease Survey 2010 rates migraine as the seventh highest specific cause of disability worldwide. Annually, migraines affect approximately 15% of the adult population in the United States [10], comprising approximately 33 million adults. Approximately 62% of migraineurs have one or more attack per month, and approximately 25% have one or more per week [11]. Approximately 80% of individuals are unable to work or function normally during a migraine attack, with 53% reporting severe impairment and/or requiring bedrest [12, 13]. Comorbid conditions associated with migraine include depression, anxiety and cardiovascular disease [14].

While there are multiple classes of medications for the acute treatment of migraine, considerable unmet need remains, as evidenced by migraines being the seventh leading cause of disability worldwide [9]. In part, this burden is attributed to limitations of current standard-of-care pharmacotherapies, which are contraindicated for use in over 2.6 million American migraine sufferers with known cardiovascular disease as well as many others with multiple cardiovascular (CV) risk factors. The US Prescribing Information (USPI) for triptans includes warnings and precautions for migraine patients with risk factors for cardiovascular disease and states that high risk patients, including those with

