3.2 Secondary

- **Freedom from Photophobia** will be assessed by tabulating the number of subjects that report the absence of photophobia at 2 hours post-dose in the subset of subjects that reported the presence of photophobia at headache baseline.
 - **Freedom from Phonophobia** will be assessed by tabulating the number of subjects that report the absence of phonophobia at 2 hours post-dose in the subset of subjects that reported the presence of phonophobia at headache baseline.
 - **Pain Relief** (aka “headache response”), at 2 hours post-dose, will be assessed using the number of evaluable subjects that report a pain level of moderate or severe (responses of 2 or 3 on the 4 point Likert scale) at baseline and then report a pain level of none or mild (response of 0 or 1) at two hours post-dose.
 - **Freedom from Nausea** will be assessed by tabulating the number of subjects that report the absence of nausea at 2 hours post-dose in the subset of subjects that reported the presence of nausea at headache baseline.
 - The probability of **requiring rescue medication** will be assessed using the number of subjects that take rescue medication within 24 after administration of study medication (BHV3000 or placebo).
 - **Sustained pain freedom**, from 2 to 24 hours, will be assessed using the number of subjects that do not experience any headache pain through the time period of interest.
-

- **Sustained pain relief**, from 2 to 24 hours will be assessed using the number of subjects that do not use any rescue medications, and do not experience any moderate or severe headache pain through the time period of interest.
- **Sustained pain freedom**, from 2 to 48 hours, will be assessed using the number of subjects that do not experience any headache pain through the time period of interest
- **Sustained pain relief** from 2 to 48 hours, will be assessed using the number of subjects that do not use any rescue medications, and do not experience any moderate or severe headache pain through the time period of interest.
- **Pain relapse** will be assessed using the number of subjects that are pain free at 2 hours post-dose and then have a headache of any severity (response of 1, 2 or 3 on the 4 point scale) within 48 hours after administration of study medication (BHV3000 or placebo).
- The proportion of subjects able to function normally, at 2 hours, will be assessed using the number of subjects that self-report as “normal” on the **functional disability** scale.

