2.3.2 Secondary Estimands

The estimands corresponding to the secondary objectives are shown in Table 2.

The population summary for all secondary estimands is the difference in the percentage of subjects with a positive result ('risk difference') between the BHV-3000 and the Placebo treatment groups.

Photophobia Freedom at 2 hours post-dose	
mITT subjects with photophobia reported as present at migraine onset	
Percent of subjects reporting no photophobia at 2 hours post-dose	
NC=F; RM=F	
Phonophobia Freedom at 2 hours post-dose	
mITT subjects with phonophobia reported as present at migraine onset	
Percent of subjects reporting no phonophobia at 2 hours post-dose	
NC=F; RM=F	
Pain Relief at 2 hours post-dose	
mITT	
Percent of subjects who report mild or no pain at 2 hours post-dose	
NC=F; RM=F	
Nausea Freedom at 2 hours post-dose	
mITT subjects with nausea reported as present at migraine onset	
Percent of subjects reporting no nausea at 2 hours post-dose	
NC=F; RM=F	
Probability of Rescue Medication	
mITT	
Percent of subjects taking rescue medication	
None	
Functional Disability at 2 hours	
mITT	
Percent of subjects with a response of "normal" at 2 hours post-dose	
NC=F; RM=F	
Sustained Pain Freedom (2 to 24 hours; or 2 to 48 hours)	
mITT	
Percent of subjects pain free during the period of interest	
NC1=F; RM=F	
Sustained Pain Relief (2 to 24 hours; or 2 to 48 hours)	
mITT	
Percent of subjects who report no pain, or mild pain, during the period of interest	
NC1=F; RM=F	
Pain Relapse (2 to 48 hours)	
- · · · · · · · · · · · · · · · · · · ·	
mi i i subjects who report bain freedom at 2 nours post-dose	
mITT subjects who report pain freedom at 2 hours post-dose Percent of subjects who report any pain during the period of interest	

Table 2: Estimands for the Secondary Objectives

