4 SUBJECT POPULATIONS

4.1 **Population Definitions**

The following subject populations will be evaluated and used for presentation and analysis of the data:

- Enrolled subjects: patients who sign an informed consent form and are assigned a subject identification number
- Randomized subjects: enrolled subjects who receive a randomization treatment assignment from the interactive web response system (IWRS), regardless of the treatment they actually received or subsequent withdrawal from treatment
- Treated subjects: enrolled subjects who take any amount of study therapy (rimegepant or placebo)
- Modified Intent-to-Treat (mITT) subjects: Randomized subjects who are randomized only once, take study medication, have a baseline migraine of moderate to severe intensity, and who provide at least one post-baseline efficacy data point. Subjects that re-enrolled in the study, and were randomized on two or more occasions are not included in the mITT population.

4.2 **Protocol Deviations**

A protocol deviation is any variance from the approved protocol, either intentional or unintentional. The possible categories for all protocol deviation are as follows:

- Informed Consent
- Inclusion/Exclusion Criteria (specify #)
- Concomitant Medication
- SAE Reporting
- Regulatory
- Drug Storage/Preparation
- Drug Administration
- Visit Schedule

- EPro Diary Noncomplinace
- Noncompliance (i.e., trends, missed assessments).

A significant protocol deviation is any deviation that could impact subject safety or the integrity of the trial. For the purposes of this study, significant protocol deviations will be defined as the following:

- Inadequate informed consent or initiation of study procedues prior to completing the informed consent
- Enrollment of subjects not meeting the inclusion/exclusion criteria
- Unreported SAEs
- Improper breaking of the blinding of the study
- Use of prohibited medication as defined by the protocol
- eDiary non-compliance with primary and secondary endpoints (2, 24, or 48-hour post-dose assessment
- Repeated deviations of the same nature for a given site or patient
- Initiation of rescue medication(s) prior to primary endpoint at 2-hours

The sponsor, or designee, will be responsible for producing the final protocol deviation file (formatted as a Microsoft Excel file). This file will include site, subject ID, deviation date, deviation type, and a description of the protocol deviation.

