2.2 Time to First Report of Absence of Various Symptoms

For each of the following variables, two sets of Kaplan-Meier plots and tables were created:

- Time to First Report of Absence of Most Bothersome Symptom
- Time to First Report of Absence of Nausea
- Time to First Report of Absence of Photophobia
- Time to First Report of Absence of Phonophobia
- Time to First Report of Return to Normal Functioning

The first set of plots and tables was similar to those created for the time to rescue medication (using actual time). For the second set of plots, nominal (planned time point) as opposed to actual time was used for clinical event times. Censoring was measured using actual time as in all previous plots.

For both sets of analyses, the analysis population for MBS and functional disability was the set of mITT subjects. The analysis population for nausea, phonophobia, and photophobia was the subset of mITT subjects that reported the symptom as present at the onset of their study migraine. The y-axis for all plots represents the probability of the occurrence of the event of interest, and therefore are increasing from left to right.

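### Functional disability at 2 hours and the 'Return to Normal Functioning' analysis include subjects who already functioned normally at migraine onset

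*SAP*

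**What the plan says.** The 2-hour function endpoint is the share of mITT subjects who rate themselves normal, which "at 2-hours post dose will be evaluated as the endpoint of interest" (SAP 5.7.4.4). SAP Table 2 gives the same population and variable, with missing data and rescue use counted as failure. Protocol 3.2 also sets no onset condition. The endpoint is last of the eleven ranked secondary tests (SAP 5.2.5).

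To enter mITT, subjects who are randomized once and take study medication must "have a baseline migraine of moderate to severe intensity, and who provide at least one post-baseline efficacy data point" (SAP 4.1). Nothing is asked about function. Function is nevertheless rated at migraine onset and at every later pain time point (Protocol 4.3.2 and Table 1).

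The associated-symptom endpoints are built differently. They count mITT subjects "who reported the presence of the symptom at migraine onset who then report the absence of the symptom at 2 hours post-dose" (SAP 5.7.4.1). Appendix 3 keeps that restriction in the sustained and time-to-event analyses of nausea, photophobia and phonophobia. For the time-to-event set, however, "the analysis population for MBS and functional disability was the set of mITT subjects" (Appendix 3, section 2.2). Sustained function (Appendix 3, section 1.4) and function at 24 hours (SAP 5.7.6.1 and Table 3) also use all mITT.

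SAP 5.7.6.5 lists functional disability twice: once in a tabulation of all mITT subjects, and once in a tabulation whose denominator is subjects reporting the symptom at baseline.

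**The concern.** Pain needs no onset condition because mITT entry already guarantees moderate or severe pain. Nothing guarantees impaired function. A subject rated normal before dosing who is still normal at 2 hours, with data and without rescue, counts as a success although no function was regained.

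The problem is sharper in the time-to-event version. A subject who never left normal functioning cannot return to it, yet is given an event at the first post-dose 'normal' entry. The curve and the median then mix recovery with subjects who were never impaired, and the label describes only recovery.

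For the ranked test, what may be at stake is sensitivity. If a sizeable share is normal at onset and treatment does little in that group, both arms' rates rise together, the difference shrinks and power falls.

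**Working it through.** **The plan's own figures.** The plan claims more than 95% power for each co-primary endpoint with about 550 per arm, and at least 90% jointly (SAP 5.1). Pain freedom of 31.4% vs 15.3% (Protocol 1.3.2.8) gives power above 99.9% at 550 per arm, and the joint bound is 0.95 + 0.95 − 1 = 0.90. The 90% treated share gives 0.90 × 600 = 540, close to the stated 550. The freedom-from-MBS rates behind the other claim are not given. No rate or power is stated for function, so the rates below are assumptions.

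**Inputs.**
- n = 550 per arm, 1:1 allocation, two-sided alpha 0.05 (documents).
- q = share of mITT normal at onset. The documents do not give it. The only related figure is in Protocol 1.4: "Approximately 80% of individuals are unable to work or function normally during a migraine attack". That suggests at most about 20% normal in migraine generally. It is not an mITT figure, and dosing here waits for moderate or severe pain, so q is run from 2% to 20%.
- Among subjects impaired at onset, 33% vs 24% are normal at 2 hours (assumed).
- Among subjects normal at onset, 90% in both arms are still normal at 2 hours (assumed). As a counter-case, 80% on rimegepant vs 70% on placebo.

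**Formulas.**
- All-mITT rate in an arm = q·s + (1 − q)·p, where s is that arm's share staying normal and p its rate among impaired subjects; n = 550.
- Restricted analysis: rate p, n = 550·(1 − q).
- Power = Φ{[d − 1.96·√(2p̄(1 − p̄)/n)] / √([pT(1 − pT) + pC(1 − pC)]/n)}, where d is the difference and p̄ the mean of the two rates.

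**Example, q = 10%.** The all-mITT rates are 0.10 × 0.90 + 0.90 × 0.33 = 0.387 and 0.10 × 0.90 + 0.90 × 0.24 = 0.306, so d = 0.081. Power = Φ[(0.081 − 1.96 × 0.0287)/0.0286] ≈ 81%. Restricted, n = 495 and d = 0.09: Φ[(0.09 − 1.96 × 0.0287)/0.0286] ≈ 88%.

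| Normal at onset | Difference, all mITT (points) | Power, all mITT | Power, impaired at onset | Power, all mITT, if 80% vs 70% stay normal |
|---|---|---|---|---|
| 2% | 8.8 | 89.4% | 90.7% | 90.8% |
| 5% | 8.6 | 86.3% | 89.8% | 90.3% |
| 10% | 8.1 | 80.7% | 88.1% | 89.5% |
| 20% | 7.2 | 68.1% | 84.2% | 88.3% |

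The restricted difference is 9.0 points throughout. Under other assumed rates (20 vs 28%, 20 vs 30%, 30 vs 38%, 30 vs 40%), with 60% to 100% of onset-normal subjects staying normal equally in both arms, the loss is about 1–2 points of power at q = 2%, 2–5 at 5%, 4–11 at 10% and 10–21 at 20%.

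**Return analysis.** Suppose every onset-normal subject reports 'normal' at the first post-dose entry, and ignore censoring. The all-mITT median falls where q + (1 − q)·F = 0.5, with F the share of impaired subjects who have recovered, so F = (0.5 − q)/(1 − q):
- q = 5%: 0.45/0.95 = 47.4%.
- q = 10%: 0.40/0.90 = 44.4%.
- q = 20%: 0.30/0.80 = 37.5%.

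The reported median is therefore reached before half of the impaired subjects have recovered. This needs no assumption about treatment effect.

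**The case against.** The 2-hour endpoint matches its stated objective. Protocol 2.2 asks about the ability to function normally at 2 hours, which is a state and not a recovery. Protocol 3.2 restricts the symptom endpoints in the same list in which it leaves function unrestricted. That stands: for the ranked test, all mITT is the protocol's definition.

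A reader might infer that the definition dilutes the effect and costs power as a matter of fact. The documents do not support that. They give neither the onset share nor any functional rate, and the loss is about 1 point at 2%. Nor are onset-normal subjects automatic successes, since they can worsen, miss the entry or take rescue. If rimegepant prevents decline, the all-mITT test captures a benefit that the restricted one discards, and the last column of the table shows the ordering reversed. That reversal is demanding, though. With 80% of onset-normal placebo subjects staying normal, rimegepant would have to add about 8 to 9 points in that group (for q of 5% to 20%) before the two analyses had equal power, which is close to the 9 points assumed among impaired subjects.

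The consequence is also limited. Function is last in the hierarchy, no power is claimed for it, and the return, sustained and 24-hour analyses lie outside the hierarchy. None of this answers the return analysis, whose name and event definition presuppose impairment at onset.

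**Conclusion.** The structural point holds. Both analyses include subjects normal at onset, although the onset rating is collected and the SAP applies an onset condition to the parallel symptom analyses. In the return analysis this is a defect of definition whenever any mITT subject is normal at onset: events are counted that are not returns, and the curve and median move early.

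For the rank-11 test the point concerns interpretation and, conditionally, sensitivity. Under the base assumptions, the power lost against a restricted analysis runs from about 1 point at 2% normal at onset to about 16 points at 20%. It requires a non-trivial onset-normal share and little treatment effect in that group. A reader might also conclude that the test is invalid or that its population must be replaced. Neither follows: the randomized comparison and type I error are intact, and the all-mITT definition comes from the protocol.

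**What to change.** 1. In Appendix 3, section 2.2, restrict the return-to-normal analysis to mITT subjects rated as mild impairment, severe impairment or bedrest at onset, as is already done there for nausea, photophobia and phonophobia.
2. Keep the all-mITT test at rank 11. Add to SAP 5.7.4.4 a supplementary analysis in subjects impaired at onset, outside the hierarchy, and tabulate onset function by arm. Do the same for function at 24 hours (5.7.6.1) and sustained function (Appendix 3, section 1.4).
3. In SAP 5.7.6.5, state which denominator applies to functional disability in each of the two tabulations.

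The cost is a few extra tables and a somewhat smaller denominator (2% to 20% smaller over the range shown). No new data are needed. Onset function is rated before dosing, so the restricted comparison remains between randomized groups. Appendix 3 is written largely in the past tense. If treatment codes were already open, the additions should be labelled post hoc; if not, they can be pre-specified.

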5.7.4.5 Sustained Pain Freedom from 2 to 24 Hours

Sustained pain freedom is assessed using the number of mITT subjects that experienced no headache pain (response of 0 on Likert scale) at all time points from 2 through 24 hours postdose. Subjects with missing pain scores at 1 or fewer time points, given that they have responses of no pain (response of 0 on 4-point Likert scale) at all other time points including the 2 and 24 hour post-dose time points will be considered as successes. Subjects with responses missing at greater than 1 post-dose time point, missing data at the 2 or 24 hour time point, or with any pain score greater than 0 will be considered as failures.

The results to be presented for the analysis include those described in items (a) through (e) for the primary analysis of pain freedom (Section 5.7.3.1). In this case, the "risk" is the probability of sustained pain freedom from 2 to 24 hours.

